10.3 Sample Processing

Anti-coagulated whole blood samples (one 10 ml green-top tube) will be processed by centrifugation for 10 minutes at 1500 x g at 4°C. The resulting plasma will be transferred to appropriately labeled polypropylene tubes and frozen at < -70°C until analysis.

10.4 Analytical Method

For analysis of ribociclib in human plasma, a sensitive and selective LC/MS/MS method will be developed and qualified in the Analytical Pharmacology Core Facility at the City of Hope. The method will be based on the published method of Kala et al.[25]

10.5 Pharmacokinetic Data Analysis Methods

Average plasma C_{trough} will be calculated for each subject and the population results will be summarized using standard statistical methods.

11. STUDY CALENDAR

All procedures may increase in frequency if clinically indicated.

Table 11.0 Study Activity Calendar

Evaluations & activities	Screening ^a	Treatment ^b							Off Tx	30-days post-last dose ^f	Long-Term Follow-Up
		Cycles 1			Cycle 2			Cycles 3+			
		Day 1 ^{c,d}	Day 8	Day 15 ^e	Day 1	Day 8	Day 15	Day 1 ^d			
MD Evaluation	X	X		X	X		X	X	X		
Informed consent ^g	X										
Eligibility criteria ^h	X										
Registration ⁱ	X										
Medical history ^j	X										
Vital signs ^k	X	X		X	X		X	X	X		
Physical exam ^l	X	X		X	X		X	X	X		
Performance status ^m		X		X				X	X	X	
Hematology	X ⁿ	X		X	X		X	X	X		
Chemistry (including LFTs)	X ⁿ	X		X	X		X	X	X		
Lipid Panel	X							X ^{gg}			
Urinanalysis / BUN	X										

Blood banking sample ^p		X								
Pharmacokinetic blood draw		X	X	X	X	X	X			
Concomitant meds ^q	X	X			X			X	X	X
AE evaluation ^r	X	X	X	X	X	X	X	X	X ^s	
Pill diary ^t		X ^t			X ^t			X ^t	X ^{hh}	
Geriatric assessment ^u		X ^v						X ^w	X ^{hh}	
WIWI and OTU x									X ^{hh}	
Radionuclide Bone Scan, Whole Body	X ^y							X ^z		
CT ^{aa}	X ^y							X ^w		
ECG (12-lead)	X			X	X		X			
Disease/Response Assessment ^{bb}								X ^w		
Ribociclib ^{cc}		Orally once daily on Days 1-21 of each cycle (See Section 5.3)								
AI ^{cc}		Per treating investigator's discretion. Dosing per package insert in each cycle. (See Section 5.3)								
Chart review dd									X dd	
Survival ^{ee}									X ee	

- a. Screening procedures to be performed within 28 days from start of protocol therapy, except labs which are to be performed within 14 days of start of study agents (footnotes 'n').
- b. Treatment will last until unacceptable toxicity or disease progression (see [Section 5.4](#) for more comprehensive list).
- c. Cycle 1 Day 1 will be defined as the day the participant initiates the combined ribociclib and endocrine therapy regimen.
- d. Each treatment cycle lasts 28 days, with a fixed window of \pm 2 days for participant convenience. The cycle duration does not change, even if ribociclib is held (Note: exceptions under certain circumstances are permitted; see [Section 6.2](#)). Day 1 safety assessments must be performed and reviewed within 48 hours of initiating ribociclib during a new cycle.
- e. Windows for Day 8 and 15 assessments are \pm 2 days.
- f. A contact/visit for review of adverse events, performance status (see [Appendix A](#)), and concomitant medication review, is to be performed at 30 ± 2 days after the last study drug is given. In lieu of a clinic visit, this may be performed via documented phone conversation with a study nurse or clinician. All participants will be followed until resolution or stabilization of all events requiring expedited reporting and occurring during treatment or starting within 30 days of last study drug.
- g. Informed consent process to be fully documented (see [Section 17.4](#)). Informed consent must occur prior to any research only (non-SOC) screening procedures.
- h. Eligibility criteria: refer to [Section 3.0](#). The site will maintain a screen-failure log for all persons screened for eligibility (see [Section 4.3](#)).
 - i. See [Section 4.2](#) for registration process. The DCC must be notified of all persons who sign consent, including screen failures or participants who fail to initiate protocol therapy (see [Section 4.3](#)).
 - j. Medical history: to include any ongoing medical conditions and medical history pertaining to eligibility on study and involvement during study.
 - k. Vital signs: Weight, heart rate, blood pressure, respiration rate, and temperature. Height required only at baseline.
 - l. Physical exam to include Clinical Evaluation of Superficial Disease for use in disease evaluation.
 - m. See [Appendix A](#) for Karnofsky performance status.
 - n. CBC and metabolic panel to be performed within 14 days prior to start of protocol therapy.
 - o. Metabolic panel: electrolytes, BUN, creatinine, AST, ALT, total bilirubin, total protein, albumin, alkaline phosphatase, and glucose).
 - p. From participants who consent to research samples only, 10 mL blood sample to be collected in a lavender (K-purple (EDTA) or green (Heparin) top tube, inverted several times, placed on ice and stored at -80°C . See [Section 9.1](#) and [Appendix D1](#).
 - q. Concomitant medications: All prescription and over-the-counter medications that have been taken within 30 days prior to the first dose of protocol therapy up to 30-day post-last dose will be recorded in the CRFs. See [Section 5.7.1](#) for concomitant medication restrictions.
 - r. Adverse events (AEs) experienced by participants will be collected and recorded from the pre-treatment Cycle 1 Day 1 safety assessments up to 30 days of the last dose of study medication. See [Section 7.0](#) for reporting guidelines). AEs will be recorded by MD on C1D1, C1D15, C2D1, C2D15, and C3D1. AEs will be recorded by RN on C1D8 and C2D8.
 - s. The period for collection, recording and reporting of AEs is extended for participant with ongoing adverse events requiring expeditious reporting (see [Section 7.3](#)).
 - t. Ribociclib pill diary: The participant will be given a pill diary (see [Appendix E](#)) which will be reviewed for adherence. It will **not be a deviation** if the diary is not returned prior to initiation of the subsequent cycle.
 - u. Geriatric Assessment (GA) to be administered either via paper (from PDF supplement) or tablet data entry. Duration for completion is usually between 20 and 40 minutes. [Appendix F](#) details the GA content, but is not for administration.

- v. GA to be administered within seven days of Cycle 1 Day 1 protocol therapy. GA will not be administered for Cycle 2 Day 1.
- w. GA and CT to be performed prior to Cycle 3 (\pm 7 days), then every 3 cycles (\pm 7 days).
- x. Was It Worth It (WIWI) Questionnaire (See [Appendix G](#) for content only but not for administration, a separate PDF can be requested from the lead study team) and Overall Treatment Utility (OTU) Questionnaire (See [Appendix H](#)).
- y. Imaging to be performed within 28 days prior to enrollment.
- z. Post-baseline radionucleotide imaging to be performed only as clinically indicated or to confirm complete response.
 - aa. CT of chest, abdomen, pelvis, any clinically indicated sites of disease, and of bone lesions.
 - bb. Confirmatory scans following documentation of progression or response will not be required; progression/response will be determined based on results of the single time point. See [Section 11.0](#).
 - cc. Refer to [Section 6.2](#) for dose modification/ dose delay guidelines.
 - dd. Medical chart review for disease progression/response will also occur until progression or the initiation of a new therapy at least twice annually or as requested by the lead study team. Post-study new therapy regimens will be collected.
 - ee. Survival analysis will be conducted by the site and/or by the lead study coordinator at least annually or as requested by the lead study team. All patients will be followed for survival information. The following will be collected: the participant's first and last name, middle initial, social security number, date of birth, and gender. The investigators will utilize the Social Security Death Index and the National Death Index to establish survival status.
- ff. ECG to be initiated at baseline mid-cycle of cycle 1 and beginning of cycle 2. Based in observed QT prolongation during treatment, ribociclib may require dose interruption, reduction or discontinuation.
- gg. Every 4th cycle.
- hh. Off Tx questionnaires to be completed within 30 days of date patient is taken off treatment or before the patient begins a new treatment, whichever occurs first.

12.0 ENDPOINT EVALUATION CRITERIA/MEASUREMENT OF EFFECT

Response and progression will be evaluated in this study using the new updated international criteria proposed by the Response Evaluation Criteria in Solid Tumors (RECIST) Committee version 1.1.[26] Per the new RECIST criteria, as disease response is not the primary endpoint of this trial, confirmatory scans following documentation of progression or response will not be required. Rather, progression/response will be determined based on results of the single scan.

12.1 Definitions

Evaluable for toxicity:

All patients will be evaluable for toxicity from the time of their first treatment with ribociclib.

Evaluable for objective response:

Only those patients who have measurable disease present at baseline, have received at least one cycle of therapy, and have had their disease re-evaluated will be considered evaluable for response. These patients will have their response classified according to the definitions stated below. (Note: Patients who exhibit objective disease progression prior to the end of cycle 1 will also be considered evaluable.)

12.2 Disease Parameters

Measurable disease:

Measurable lesions are defined as those that can be accurately measured in at least one dimension (longest diameter to be recorded) as >10mm with conventional techniques (CT, MRI, or caliper measurement) and as >20mm by chest X-ray (if clearly defined and surrounded by aerated lung.) Lymph nodes greater than 10mm on short axis are considered measurable as well. All tumor measurements must be recorded in millimeters (or decimal fractions of centimeters).

Non-measurable disease:

All other lesions (or sites of disease), including small lesions (longest diameter <20 mm by chest X-ray or <10 mm using CT, MRI or caliper measurement), are considered non-measurable disease. Organomegaly, leptomeningeal disease, ascites, pleural/pericardial effusions, lymphangitis cutis/pulmonis, inflammatory breast disease, and abdominal masses (not followed by CT or MRI) are all non-measurable.

Bone-Only Disease:

No distant metastases other than in bone.

Target lesions:

All measurable lesions up to a maximum of 2 lesions per organ and 5 lesions in total, representative of all involved organs, should be identified as target lesions and recorded and measured at baseline. Lymph nodes less than 15mm in the short axis cannot be used as target lesions. Target lesions should be selected on the basis of their size (lesions with the longest diameter) and their suitability for accurate repeated measurements (either by imaging techniques or clinically). A sum of the longest diameter (LD) for all target lesions will be calculated and reported as the baseline sum LD. The baseline sum LD will be used as reference by which to characterize the objective tumor response.

Non-target lesions:

All other lesions (or sites of disease) including any measurable lesions over and above the 10 target lesions should be identified as non-target lesions and should also be recorded at baseline. Measurements of these lesions are not required, but the presence or absence of each should be noted throughout follow-up.

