12.4 Response Criteria

12.4.1 Evaluation of Target Lesions

Complete Response (CR):	Disappearance of all target lesions. Lymph node CR is when the lymph node has decreased to less than 10mm in the short axis.
Partial Response (PR):	At least a 30% decrease in the sum of the longest diameter (LD) of target lesions, taking as reference the baseline sum LD
Progressive Disease (PD):	At least a 20% increase in the sum of the LD of target lesions, taking as reference the smallest sum LD recorded since the treatment started (including the baseline scan if that is the smallest), and at least a 5mm increase or the appearance of new lesions.
Stable Disease (SD):	Neither sufficient shrinkage to qualify for PR nor sufficient increase to qualify for PD, taking as reference the smallest sum LD since the treatment started.

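### Section 12's tumour-measurement rules (target cap, node size, node axis) are inconsistent and can misclassify objective response, a secondary endpoint

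*Combined protocol and SAP*

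**What the plan says.** All the rules are in Section 12 of the combined protocol and SAP.

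- **Number of targets (12.2).** Targets are "All measurable lesions up to a maximum of 2 lesions per organ and 5 lesions in total". The definition of non-target lesions, which follows directly, refers to "any measurable lesions over and above the 10 target lesions".
- **Node size (12.2).** "Lymph nodes greater than 10mm on short axis are considered measurable as well", but "Lymph nodes less than 15mm in the short axis cannot be used as target lesions".
- **Who is evaluable for response (12.1).** "Only those patients who have measurable disease present at baseline, have received at least one cycle of therapy" and have been re-assessed. Having a target lesion is not a condition.
- **Axis (12.4.1).** "Lymph node CR is when the lymph node has decreased to less than 10mm in the short axis". PR, however, is "At least a 30% decrease in the sum of the longest diameter (LD) of target lesions", and PD is a rise in the same longest-diameter sum. SD is "Neither sufficient shrinkage to qualify for PR nor sufficient increase to qualify for PD".
- **Overall response (Table 12.4.3).** Every row leading to CR, PR or SD starts from a target-lesion status of CR, PR or SD. The only rows open to any target status lead to PD.

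Section 13.4 reports objective response (CR+PR) and clinical benefit (CR+PR+SD) with exact binomial limits.

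**The concern.** These are working rules for a planned endpoint. A radiologist has to decide how many lesions to measure, whether a small node can be a target, and which diameter to enter in the sum, and on each question the section gives two answers or leaves a gap. Sections 12 and 12.4.3 let a single scan settle response, without confirmation, and describe no central reading. The synopsis lists several sites. A difference in reading would therefore pass straight into the response rate. At stake are the PR or SD status of individual patients and the make-up of the response denominator.

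**Working it through.** **Plan's own figures.** The plan gives no figure for response precision. Its design figures in 13.2 concern toxicity, and they reproduce: exact limits for 20/40 are 0.338 to 0.662 (stated 0.34 and 0.66), and 1 - 0.95^40 = 0.871 (stated 87 in 100). They are not in dispute.

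**1. Five or ten targets.** Inputs are the cap of 5, the reference to 10, the limit of 2 per organ (the only per-organ limit given, so applied under both readings) and the 30% PR threshold. The two readings differ only if a sixth lesion could be a target. At 2 per organ, that needs at least six eligible lesions in at least three organs. The lesion sizes below are hypothetical.

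- Six lesions, two in each of three organs. Baseline 30, 28, 26, 24, 22, 20 mm; follow-up 21, 19, 18, 16, 15, 20 mm.
  - Largest 5 as targets: 130 to 89 mm, (89 - 130)/130 = -31.5%. The sixth lesion is an unchanged non-target, so the table gives PR.
  - All 6 as targets: 150 to 109 mm, (109 - 150)/150 = -27.3%, which is SD.
- The switch can go the other way. Ten lesions, two in each of five organs. Baseline 40, 35, 30, 25, 20, 18, 16, 15, 14, 12 mm; follow-up 29, 25, 22, 18, 15, 9, 8, 7, 7, 6 mm.
  - 5 targets: 150 to 109 mm, -27.3%, SD.
  - 10 targets: 225 to 146 mm, -35.1%, PR.

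**2. Small nodes and evaluability.** Take a patient whose only disease is nodes over 10 mm and under 15 mm short axis.

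- 12.2: the disease is measurable.
- 12.1: after one cycle and a re-assessment, the patient is evaluable for response.
- 12.2: none of the nodes may be a target, so there are 0 targets and no baseline sum.
- 12.4.1: PR needs a 30% fall in that sum, so PR cannot be reached.
- Table 12.4.3: no CR, PR or SD row applies; only the PD rows can.

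**3. Short axis or longest diameter.** Illustration with two targets: a liver lesion going from 30 to 22 mm, and a node going from 28 x 16 to 24 x 9 mm. The node qualifies as a target at baseline (short axis 16 mm) and is in CR at follow-up (short axis 9 mm).

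- Longest diameters, as written: 30 + 28 = 58 to 22 + 24 = 46 mm, -12/58 = -20.7%, SD.
- Short axis for the node: 30 + 16 = 46 to 22 + 9 = 31 mm, -15/46 = -32.6%, PR.

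As written, a node already in CR still adds 24 mm to the sum.

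**4. Effect on the response rate.** One reclassified patient moves the rate by 1/n.

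- n = 40: 2.5 points. For example, 16/40 = 40.0% (exact 95% limits 24.9 to 56.7) against 15/40 = 37.5% (22.7 to 54.2).
- n = 30: 3.3 points. For example, 12/30 = 40.0% (22.7 to 59.4) against 11/30 = 36.7% (19.9 to 56.1).

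The value 30 is an assumption. The synopsis admits bone-only disease as an alternative to measurable disease, so the response denominator may fall below 40, but the plan gives no number.

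**The case against.** The strongest reply is that these are slips with a natural reading.

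- **The cap.** Five is the only explicit selection rule; the 10 appears in passing, in the definition of what is left over. This stands: 5 is very likely intended, and nothing shows that a reader would measure ten lesions against an explicit limit of five.
- **The node sizes.** A lesion can be measurable without being a target, and the non-target definition already takes in all other lesions, so nodes between 10 and 15 mm are non-target. This also stands: the two thresholds do not contradict each other by themselves. The gap is that evaluability rests on the lower threshold, while the response table assumes a target exists.
- **The axis.** Node CR is a size threshold, while PR and PD are changes in a sum. These are different quantities, so there is no strict contradiction. The consequence shown in step 3 remains.
- **The reference to RECIST 1.1.** It might be said to settle all three points. But 12.1 says that patients are classified by the protocol's own definitions, and the objectives refer to a modified RECIST 1.1 without saying what was modified. A reader cannot tell which departures are deliberate.

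A reader might also infer more than the text supports:

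- *That clinical benefit shifts with the lesion count.* A switch between PR and SD cannot change it, because both count as benefit.
- *That progression-free survival rests on the target sum.* Its definition in 13.1.5 lists recurrence, contralateral disease, second primary and death, and does not cite the sum.
- *That patients with only small nodes can never respond.* Section 12.4.2 defines CR for non-target lesions. What is missing is a table row that turns it into an overall response.
- *That such patients will be enrolled.* The documents show only that they can be.

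**Conclusion.** Wrong as written, minor. Section 12 can assign PR or SD to the same measurements depending on which lesion count is used. It can place a patient in the response denominator with no target sum and no applicable CR, PR or SD row. It also keeps the full length of a node already in CR within the sum. Each affected patient moves the objective response rate by about 2.5 points (n = 40) to 3.3 points (n = 30, assumed), which is small beside an exact interval of about 25% to 57% for 16/40. The number of patients affected is unknown: the documents do not say how many will have six or more eligible lesions in three or more organs, or only nodes between 10 and 15 mm. The patient examples are illustrations and do not estimate frequency. The primary toxicity endpoint and N = 40 are unaffected.

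**What to change.** Edit Section 12 before response is analysed:

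1. In the non-target definition (12.2), change 10 target lesions to 5, to match the cap.
2. In 12.1, require at least one target lesion for objective-response evaluability. Alternatively, in 12.2, call nodes measurable only at 15 mm or more short axis.
3. Add to Table 12.4.3 a classification for patients with non-target disease only, using the categories already in 12.4.2.
4. In 12.2 and 12.4.1, use the short axis for nodes in the target sum, as target eligibility and node CR already do.

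The cost is a few wording edits. No extra imaging is needed and the sample size does not change.

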12.3 Methods for Evaluation of Measurable Disease

All measurements should be taken and recorded in metric notation using a ruler or calipers. All baseline evaluations should be performed as closely as possible to the beginning of treatment and never more than 30 days before the beginning of the treatment.

The same method of assessment and the same technique should be used to characterize each identified and reported lesion at baseline and during follow-up. Imaging-based evaluation is preferred to evaluation by clinical examination when both methods have been used to assess the antitumor effect of a treatment.

Clinical lesions:

Clinical lesions will only be considered measurable when they are superficial (e.g., skin nodules and palpable lymph nodes). In the case of skin lesions, documentation by color photography, including a ruler to estimate the size of the lesion, is recommended.

Chest x-ray:

Lesions on chest x-ray are acceptable as measurable lesions when they are clearly defined and surrounded by aerated lung. However, CT is preferable.

Conventional CT and MRI:

These techniques should be performed with cuts of 10 mm or less in slice thickness contiguously. Spiral CT should be performed using a 5 mm contiguous reconstruction algorithm. This applies to tumors of the chest, abdomen, and pelvis. Head and neck tumors and those of extremities usually require specific protocols such as CT head and neck or MRI brain.

Ultrasound (US):

When the primary endpoint of the study is objective response evaluation, US should not be used to measure tumor lesions. It is, however, a possible alternative to clinical measurements of superficial palpable lymph nodes, subcutaneous lesions, and thyroid nodules. US might also be useful to confirm the complete disappearance of superficial lesions usually assessed by clinical examination.

Endoscopy, Laparoscopy:

The utilization of these techniques for objective tumor evaluation has not yet been fully and widely validated. Their uses in this specific context require sophisticated equipment and a high level of expertise that may only be available in some centers. Therefore, the utilization of such techniques for objective tumor response should be restricted to validation purposes in reference centers. However, such techniques may be useful to confirm complete pathological response when biopsies are obtained.

Tumor markers:

Tumor markers alone cannot be used to assess response. If markers are initially above the upper normal limit, they must normalize for a patient to be considered in complete clinical response.

Cytology, Histology:

These techniques can be used to differentiate between partial responses (PR) and complete responses (CR) in rare cases (e.g., residual lesions in tumor types, such as germ cell tumors, where known residual benign tumors can remain).

The cytological confirmation of the neoplastic origin of any effusion that appears or worsens during treatment when the measurable tumor has met criteria for response or stable disease is mandatory to differentiate between response or stable disease (an effusion may be a side effect of the treatment) and progressive disease.

